2.1.3 Primary and Secondary Aims

Primary Aims: To determine the feasibility and acceptability of an RCT comparing two VEGA educational approaches, the self-directed vs facilitator-led VEGA, in HHSPs who serve veterans and their families. To determine the feasibility of the RCT we will use four outcomes: (i) the number of HHSPs who meet eligibility criteria and (ii) who agree to be randomized to either self-directed or facilitator-led VEGA education approaches, both overall and per week of recruitment, (iii) the proportion of HHSPs who complete each arm, with completion consisting of the review of all module content and the animated simulations in the case of self-directed VEGA and full attendance of the virtual workshop in the case of facilitator-led VEGA and (iv) the feasibility of collecting trial outcome data at Time 1, Time 2, and Time 3. The acceptability of the facilitator-led and self-directed educational approaches as well as their value and impact will be determined via the coding of qualitative interview data from a sub-sample of participants.

Our aims are that (i) we will recruit, on average, 5 providers per week and achieve our sample aims of 80 participants within 16 weeks, (ii) the proportion of providers who contact the research team about participation and who consent to randomization will be 70% or greater, (iii) the proportion of providers who are randomized and complete their assigned intervention will be 70% or greater for each arm and (iv) the proportion of missing data for each time-point will be less than 20%.

Centre of Excellence VEGA Training and Research Project

As of March 2023, we will revise primary outcomes (ii) and (iii) to (ii) the number of HHSPs who consent to participate in the study and complete self-directed VEGA, both overall and per week of recruitment, (iii) the proportion of HHSPs who complete self-directed VEGA, with completion consisting of the review of all module content and the animated simulations in the case of self-directed VEGA. Our aims are (ii) the proportion of providers who contact the research team about participation and who consent to participate will be 70% or greater and (iii) the proportion of providers who complete self-directed VEGA will be 70% or greater.

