2.2.2 Informed Consent

Once a provider has initiated contact with the research team, the research assistant (RA) will, depending on the participant's preference, either arrange a telephone call to discuss the study and ask eligibility and demographic screening questions or send them a link to the screening & demographics questionnaire hosted on REDCap [see “Step 3: Initial Contact from Participant & Arranging Screening and Demographics Questionnaire” in “CoE_VEGA_EmailScripts_V8_12MAY2023”]. During the call, the RA will first give a short description of the training and research components of the study with the opportunity of providers to ask questions. If participants choose to self-complete the questionnaire online, there will also be a short description of the study before participants complete the questionnaire on REDCap. The screening and demographics questionnaire will contain a series of questions to determine the eligibility of providers for the study, defined by the inclusion and exclusion criteria above. It will also ask a series of sociodemographic questions [for eligibility and demographic questions, see “Appendix A: Screening Eligibility and Demographic Questionnaire REDCap Form” in “CoE_VEGA_ScreeningCallScript_V7_03APR2023”]. If completing measures over the phone, the provider's answers will be entered by the RA into REDCap. We will obtain written consent from providers to keep their responses to the screening and demographics questionnaire should they end up being ineligible or do not end up participating in the study. This is for the purpose of comparing those who end up participating to those who do not end up participating to understand

Centre of Excellence VEGA Training and Research Project

if our criteria are potentially excluding a particular group of people or if those who do not end up participating belong to a particular group.

After completing the eligibility and demographic questions, providers will be informed of their eligibility for the study. This communication will occur via phone [see pg. 2-3 of CoE_VEGA_ScreeningCallScript_V7_03APR2023] or email [see pg. 4-5 of CoE_VEGA_EmailScripts_V8_12MAY2023] based on the participant's preference.

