3.0 Data Collection

3.1.1 Feasibility Statistics

The RC will keep track of the number of providers who: (a) agreed to be screened; (b) are eligible for participation; and (c) enroll. We will also record the number of: (d) emails/phone calls needed to arrange all research assessments; (e) participants who drop out; participants who (f) could not be reached for follow-up; (g) complete the intervention; and (h) partially complete vs. fully complete research assessments for our Primary Objectives. As an indicator of feasibility, we will also record the total time to complete all quantitative assessments.

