3.1.2 Quantitative Assessments

A trained research assistant (RA) will gather all data from all participants during three study assessment time points. Quantitative assessments will be hosted on REDCap and will be available online using a web-based link and emailed to participants at three time points: the week before they begin the VEGA training (Time 1), post-education (Time 2), and 3-months after the Time 1 survey is completed (Time 3). Participants will be asked to complete the surveys within one week, from the date they are initially sent, on their own time. Time 1 surveys will be sent

Centre of Excellence VEGA Training and Research Project

after completing the consent form, Time 2 will be sent the day after the online modules are due to be completed (experimental arm), and Time 3 will be sent 3 months after this date, to be completed within two weeks. Each survey will take approximately 30 minutes to complete. A detailed list and description of study measures can be found below. The format of all of surveys, listing all of the questions in each questionnaire can be found in [“CoE_VEGA_QuantitativeSurvey_V3_12MAY2022”]. Due to changes in requirements for continuing education credits, we created an alternative version of the survey [“CoE_VEGA_QuantitativeSurveyB_V3_24MAR2023”] that excludes the measures “Child Maltreatment Knowledge and Skills Questions developed by the VEGA team” and “Satisfaction with VEGA training” because the VEGA team will administer questions required for continuing education credits. As of March 2023, all participants in the study will be administered this version [CoE_VEGA_QuantitativeSurveyB_V3_24MAR2023], we will not be administering the original version [CoE_VEGA_QuantitativeSurvey_V3_12MAY2022]. As a courtesy, participants will also have the option of completing the surveys in either English or French. Before each survey, they will be asked if they would like to complete the current survey in English or French.

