4.0 Statistical Analyses

4.1 Quantitative Analyses

4.1.1 Sociodemographic Characteristics: Descriptive statistics (means, standard deviations, relevant quantiles, and proportions) will be used to report the sample of HHSP's sociodemographic characteristics.

4.1.2 Primary Outcomes: Descriptive statistics (totals, means, standard deviations) will be used to compare primary outcomes to a priori thresholds for acceptability and feasibility outlined in section 2.1.2 Primary Aims.

4.1.3 Secondary Outcomes: Our secondary outcomes will be analyzed via generating bivariate correlations and regression coefficients for variables we hypothesize to be mediators, moderators, and outcomes for a definitive trial.

4.1.4 Missing Data: We will use a force-choiced framework in REDCap in to reduce the possibility of missing data..

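### The primary feasibility thresholds cannot be scored unambiguously as written, and with about 40 participants a bare pass carries little assurance

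*Combined protocol and SAP*

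**What the plan says.** Since March 2023 the study has been a one-arm pilot of 40 providers (4.2). The current text of 2.1.3 sets these targets:

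- Aim (ii): "the proportion of providers who contact the research team about participation and who consent to participate will be 70% or greater".
- Aim (iii): "the proportion of providers who complete self-directed VEGA will be 70% or greater".
- Aim (iv), unchanged: "the proportion of missing data for each time-point will be less than 20" per cent.

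The same section revises outcome (ii) to a number: those who consent and also finish the self-directed modules.

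On the counts, 3.1.1 states: "The RC will keep track of the number of providers who: (a) agreed to be screened; (b) are eligible for participation; and (c) enroll". It goes on to list dropouts, participants not reached, intervention completion, and partial versus full assessments. Contacts are not listed. In 2.2.2, screening starts "Once a provider has initiated contact with the research team", so contact precedes any eligibility check.

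On Time 3, 3.1.2 first places the survey three months after Time 1 is completed and gives a general rule: "Participants will be asked to complete the surveys within one week". The next sentence but one dates it from the Time 2 mailing, which is the day after the modules are due: "Time 3 will be sent 3 months after this date, to be completed within two weeks".

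On analysis, 4.1.2 states: "Descriptive statistics (totals, means, standard deviations) will be used to compare primary outcomes to a priori thresholds". No interval or decision probability is mentioned.

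**The concern.** These are the primary outcomes, and 4.2 and 4.4 use them to judge recruitment and retention for a definitive trial and whether that trial is tenable. Two analysts with the same data should reach the same result on each target, and a met target should mean something about the underlying rate. Neither is secured.

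- **Aim (ii).** Providers found ineligible enter the denominator but can never enter the numerator. A low value could reflect narrow criteria or unwilling providers, which are different problems for a later trial. A provider who makes contact but is never screened appears in none of the listed counts.
- **Outcome (ii) against aim (ii).** One is a count that depends on completion; the other is a proportion that does not.
- **Aim (iii).** The two-arm aim used randomized providers as the base. The one-arm text drops that base and supplies no other.
- **Aim (iv).** Time 3 has conflicting dates and windows, and missing is not defined.
- **Precision.** A proportion from 40 people that sits on a cut-off is compatible with a wide range of true rates.

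**Working it through.** **The plan's own figures.** The plan gives no precision for the thresholds. Aim (i) is internally exact for the two-arm design: 5 per week × 16 weeks = 80. The 40 comes from a two-arm power statement (80% power, 0.5–0.6 SD), with alpha and sidedness not given. The detectable effect is (z_alpha + z_0.80) × √(2/40). At one-sided 5% it is 0.556 SD, inside the stated range; at two-sided 5% it is 0.626 SD, just outside. Either way, that statement concerns mean scores and says nothing about the feasibility proportions.

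**Aim (ii): what the contact denominator does.** Let e be the eligible share of contacts and c the consent rate among eligible providers. The contact-based rate is e × c, so meeting 70% needs c ≥ 0.70/e. The documents give no value for e; the values below are assumptions.

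| e | c needed for 70% | contact-based rate if c = 80% |
|---|---|---|
| 95% | 73.7% | 76% (meets) |
| 90% | 77.8% | 72% (meets) |
| 80% | 87.5% | 64% (misses) |
| 75% | 93.3% | 60% (misses) |
| 70% | 100% | 56% (misses) |

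The same willingness meets or misses the target according to e alone. Below 70% eligible, the target cannot be reached. The base for this aim is also not 40: with 40 consents, 40/57 = 70.2% meets it and 40/58 = 69.0% does not, so at most 57 contacts are allowed. The exact 95% CI for 40/57 is 56.6–81.6%.

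**Outcome (ii) against aim (ii).** If 40 consent and 28 of them complete, revised outcome (ii) is 28, while aim (ii) is 40 divided by contacts. The first cannot be compared with the second's 70%.

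**Time 3 windows.** Assumptions: three months = 91 days, and modules due 7 to 14 days after Time 1 is completed.

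- Anchor at Time 1 completion, one-week return: days 91–98.
- Anchor at the Time 2 mailing, two-week return: days 99–113 if modules are due on day 7 (8 + 91 = 99), or 106–120 if due on day 14 (15 + 91 = 106).
- If the anchor is read as the due date itself: days 98–112 or 105–119.

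The two schemes at most touch, at day 98. With modules due on day 7, a survey returned on day 105 is late under the first scheme and on time under the second.

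**Precision at N = 40** (Clopper–Pearson 95% intervals and exact binomial tails).

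- 28/40 = 70%: 53.5–83.4%.
- 7/40 = 17.5% missing, the largest count strictly below 20%: 7.3–32.8%.
- Completion target met, P(X ≥ 28): 0.129 at a true 60%, 0.314 at 65%, 0.577 at 70%, 0.821 at 75%. A true 70% therefore misses with probability 1 − 0.577 = 0.423.
- Missing-data target met at one time point, P(X ≤ 7): 0.756 at a true 15%, 0.437 at 20%, 0.182 at 25%.
- For the interval itself to clear the threshold, at least 34/40 (85%) must complete, or at most 2/40 (5%) may be missing.

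**The case against.** The best defence is that none of this is an error of calculation. Consents per contact is a legitimate recruitment-yield measure, and a conservative one. Outcome (i) and the 3.1.1 list already give eligible and enrolled numbers, so enrolled/eligible can be computed today, and 2.2.2 retains consented screening data from ineligible and non-participating providers. A miss caused by ineligibility would be visible. Contacts are probably recoverable: 2.1.1 has the coordinator tracking recruitment, and 6.2.2 shows that email and telephone records exist. The participant-flow figures are not reproduced, so they may start at contact. The two-week sentence can be read as an exception for Time 3. Section 2.1.3 sets targets rather than tests, there is no stop/go rule, and 4.4 weighs the metrics alongside interview data.

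Most of this stands, and it rules out several stronger readings that a reader might infer.

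- *The thresholds would be scored wrongly.* The text supports only that they cannot be scored unambiguously.
- *Aim (ii) will fail through ineligibility, driven by social-media and snowball recruitment.* No eligible share is given, and 2.2.1 asks source participants about people who meet the criteria. At 90% eligible and 80% consent the rate is 72%, a pass.
- *Aim (iv) passes or fails by window.* That needs late returns to count as missing, and no section says they do. Only one of three time points is involved.
- *The 70% should move to eligible providers.* That would ease a primary criterion mid-trial after low enrolment, and reporting both ratios serves the purpose.

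The defence does not answer the mismatch between outcome (ii) and aim (ii), the absent denominator in aim (iii), the two Time 3 anchors, the undefined term in aim (iv) or the lack of any interval. Recovery of contacts from correspondence is also time-limited: 6.2.2 destroys those records one month after data collection ends.

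**Conclusion.** The point holds in this form: the primary feasibility targets are open to more than one scoring, and meeting one by point estimate says little about the true rate. The precision part is firm and rests only on N = 40 and independent participants: about 15 points either side at 28/40, a 13% chance of meeting the completion target at a true 60%, and a 42% chance of missing it at a true 70%. The aim (ii) part is structural; its size depends on an eligible share the documents do not give, and it is harmless if nearly all contacts are eligible. The Time 3 contradiction affects survey timing whatever is decided about late returns, and affects aim (iv) only if they count as missing; the day counts rest on the 91-day and 7–14-day assumptions. The changes are worth making because these results are meant to inform a definitive trial.

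**What to change.** - **3.1.1:** add the number of providers who contact the team, and fill it from correspondence before those records are destroyed.
- **2.1.3, aim (ii):** keep the contact-based 70% target as the criterion and report consented/eligible beside it, without redefining the target. Align outcome (ii) with aim (ii), so that both concern consent; completion belongs to (iii).
- **2.1.3, aim (iii):** state it as completed/consented.
- **3.1.2 and aim (iv):** reconcile the passages on the Time 3 anchor and return window so that one of each applies throughout, and state whether late returns count as missing.
- **4.1.2:** report each proportion with its exact 95% CI and interpret the threshold in the light of it. An interval alone does not change the 13% and 42% figures; it shows how far a met or missed target can be trusted.

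Cost: protocol wording and one extra log column, with no new data from participants and no change to any threshold value. The downside is that a bare pass will look less certain, which is accurate.

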2.2 Sampling and Recruitment

To determine the feasibility of evaluating the effectiveness of both of VEGA's educational approaches, as well as to generate preliminary estimates of effect for sampling and effect size calculations, a two-arm pilot randomized controlled trial (RCT) will be used (28). Eligible participants will be randomly assigned to receive either self-directed (i.e., experimental) or facilitator-led (i.e., active control (AC)) VEGA. The RCT will follow the Consolidated Standards of Reporting Trials (CONSORT) guidelines and will be registered with clinicaltrials.gov, following ethics approval. The trial design is summarized in Figure 1 below.

[figure not shown]
Figure 1. Pilot Randomized Controlled Trial – Participant Flow

Centre of Excellence VEGA Training and Research Project

As of March 2023, we will be using a one-arm pilot trial. Eligible participants will be asked to complete self-directed VEGA only.

Figure 2. Pilot Trial – Participant Flow as of March 2023

2.2.1 Eligibility and Screening

Study participants will be recruited from a population of veteran-serving HSSPs working within programs, agencies, and organizations recommended by the Atlas Institute for Veterans and Families, examples include the Veteran Affairs Canada (VAC) Assistance Service, the Veteran Family Program, or the Operational Stress Injury Clinics. These contacts will be within Atlas' and the research team's professional networks. Direct recruitment of providers will also take place via social media accounts of research team members and partnering agencies [see CoE_VEGA_Social Media Drafts_V2_10APR2023]. Veteran-Serving HSSPs are eligible for inclusion if:

- i. They are healthcare or social service professionals.
- ii. They are working with military and/or RCMP veterans or military and/or RCMP veteran's family members in a direct service capacity at least one day per week OR they have at least two years or more of experience working with military and/or RCMP veterans or their family members in a direct service capacity OR they have worked with 15 or more patients that were either military and/or RCMP veterans or their family members in a direct service capacity.
- iii. They are willing and capable of providing informed, written consent and completing all project activities in English.

Exclusion Criteria: HSSPs who have previously registered to access VEGA materials; HSSPs who are currently enrolled in or expected to enroll in any other educational intervention focused on family violence (intimate partner violence, child maltreatment, childhood exposure to IPV) within the study time period.

Directors of programs and agencies/organizations recommended by Atlas as well as providers belonging to the professional networks of the teams' will be contacted by the Research Coordinator (RC) and PI via email and provided with a one-page overview of the study and the opportunity to meet with the research team to address study-related questions [see "Step 1: Initial Contact of Program Directors and Professional Contacts" in CoE_VEGA_EmailScripts_V8_12MAY2023"]. If a meeting takes place, during the meeting, the team will discuss the study with the program directors/professional contacts and program directors will be asked to sign an Expression of Interest (EOI) form [see "CoE_VEGA_EOI_V3_24MAY2022"]. The EOI form asks program directors to support (a) HSSP completion of VEGA training components, and (b) HHSPs to complete research activities outside regular work hours to receive study honoraria. The Expression of Interest form also asks program directors to confirm that the program is not currently participating in other research projects concerning family violence. During the meeting, the team will obtain verbal consent from the directors of enrolled programs to allow staff to attend study-related webinars, led by the project team, prior to the launch of recruitment efforts. Webinar content will review staff eligibility criteria, as well as recruitment and research-related procedures. Following the completion of the webinars, directors of the enrolled programs will distribute recruitment materials via email to all providers; materials will encourage interested participants to contact the research team [see "Step 2: Webinar Content and Recruitment Materials" in

Centre of Excellence VEGA Training and Research Project

“CoE_VEGA_EmailScripts_V8_12MAY2023”]. These materials include a one-page flyer that summarizes the study purpose, what the VEGA intervention is generally about, and honorarium available to participants for completing the research components [see “CoE_VEGA_OnePageFlyerB_V4_29MAR2023”]. These recruitment materials will also be available in French.

As of March 2023, after feedback from our sponsor, we are removing the request to have a meeting with directors at programs/agencies and professional contacts in our initial email script. We have replaced this with a simple request to contacts to distribute the one-page flyer attached to the email, to their network. If contacts express an interest in allowing us to present webinars to providers, we will inform them via email that the webinars are not overseen by HiREB and give them the opportunity to obtain REB approval of the slides and their content [see pg. 2 of CoE_VEGA_EmailScripts_V8_12MAY2023”].

We will also recruit using a snowball subject sampling method. Participants will be invited to share the study with their contacts to allow for an accumulation of participants over time. At the conclusion of completing the consent process, the 'source' participant will be asked if they know any other residents meeting our eligibility criteria and whom they think may be interested in participating in this study. If the participant indicates that they do know someone that may be interested and who may meet the study eligibility criteria, the source participant/participants will forward the study information letter and one-page flyer to the individual(s) so that the individual(s) can contact the research team, if they are interested in participating. It will be up to the participant as to whether or not they indicate to the individual(s) in that email as to whether or not the participant actually participated in the study.

